Both compliance with treatment and vomiting within an hour of the dose will be recorded in REDCap (along with the daily PUQE score) to evaluate these factors in the interpretation of

plasma concentrations. Mirtazapine treatment will continue unless the participant withdraws consent, experiences a limiting side effect or an obstetrician decides that the health risk to the patient compels discontinuation. At the end of the 3-week trial, subjects will be asked whether they prefer to continue mirtazapine, which will also serve as a measure of treatment satisfaction. Pregnant persons who choose to stop treatment will be given a taper regimen in reverse order of the dose escalation required for the 3-week trial. For example, if a patient is taking 45 mg at the end of week 3, she will begin a taper (by week) of 30 to 15 to 7.5 to 0 mg. If she relapses or has discontinuation symptoms, the previous effective dose will be given. She may attempt to taper again with the same approach. Participants who continue to be treated with mirtazapine in the continuation phase will be followed monthly throughout pregnancy unless they withdraw consent.

Maintenance Drug Treatment (Figure 4). For pregnant persons who choose to continue treatment, mirtazapine will be prescribed at the dose achieved at the end of the 3-week trial. The duration of treatment will be decided by the patient with a study obstetrician based upon her response and comfort with drug discontinuation. These data will be novel since no information on the duration of treatment with mirtazapine in persons with sNVP is available. For persons treated until delivery, maternal and cord blood will be obtained for plasma mirtazapine concentration measurement to evaluate placental transfer. If postpartum mirtazapine treatment is desired, it will be coordinated with our Collaborative Care Perinatal Services (COMPASS - the integrated mental health program in the Obstetrics department), or in the Asher Center in the Department of Psychiatry, which [name] directs.

Figure 4: Data Collection: Continuation Treatment					
Maintenance (every 4 weeks)	Delivery				
Wt, Ht, BP PUQE GH Plasma PHQ-9 GAD-7 C-SSRS ASE SS Medication Log	PES Maternal and umbilical cord blood				
Log PUQE=Pregnancy Unique Quality of Emesis; PHQ-9=Patient Health Questionnaire; GAD-7 =Generalized Anxiety Disorder; C-SSRS=Columbia-Suicide Severity Rating Scale; ASE=Asberg Side Effects; SS=Screen for Serotonin Syndrome. PES, Peripartum Events Scale.					

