9-Item Patient Health Questionnaire (PHQ-9)⁶⁰: The 9-Item Patient Health Questionnaire (PHQ-9) is a self-administered instrument based on the nine DSM-5 criteria listed under criterion A for Major Depressive Disorder. The questionnaire includes criteria based diagnosis of depressive symptoms, assists in identifying treatment goals, determining severity of symptoms, as well as guiding clinical intervention. When considering a diagnosis, the clinician will use clinical interviewing skills to determine whether the symptoms are causing clinically significant distress or impairment and those symptoms are not better explained or attributed to other conditions, such as substance use, medical conditions, or bereavement.

Generalized Anxiety Disorder Scale, **7-item (GAD-7)**⁶¹**:** The Generalized Anxiety Scale is a 7-item self-report for symptoms consistent with the Diagnostic and Statistical Manual of Mental Disorders of generalized anxiety disorder.

Peripartum Events Scale (PES)⁶²: The Peripartum Events Scale (PES) captures data from several categories in the birth record. The following categories of events are included: medical and obstetric risk factors, time in operating room, fetal monitoring, surgical complications, infant anthropometrics and outcome, NICU admission, and postpartum complications (such as infection, hemorrhage). Admission to the special care nursery will also

be noted. We have modified the original measure to align with current obstetrical practices. The PES will be completed for all enrolled participants.

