Authorized research personnel will work with clinicians from the Northwestern Obstetrics and Gynecology services and the Obstetrical Triage program to identify potentially eligible individuals and approach them about their interest in participating. We have defined several eligibility criteria to allow participants to be screened by our study team. Subject burden can be reduced and study efficiency improved by asking only those subjects likely to be eligible to undergo a full baseline assessment. The screen includes: 1) age 2) gestational age of the fetus, 3) confirmation of plan to receive care and deliver at Prentice Women's Hospital (PWH), 4)

PUQE score of 10-15, 5) has been treated with at least two anti-emetic/antinauseant drugs with inadequate response; and 8) English speaking.

The inclusion/exclusion criteria will be reviewed in the patient's chart and documented on the screening log. If a patient meets all the inclusion criteria for enrollment, does not have any of the exclusion criteria, she will be approached about the study by authorized personnel. Her primary obstetrician will be contacted to review the patient's participation.

Brochures will be available to provide potential subjects with additional information. We will also post information about this study on our Asher Center and Northwestern Medicine websites, as well as post on the NCT site.

COMPENSATION FOR PARTICIPATION IN RESEARCH ACTIVITIES

Participants will be compensated with \$35 for each week of the three-week trial. If a participant wishes to participate in the continuation period or a mirtazapine tapering regimen, they will continue for 5 additional weeks and compensated with \$35 each week.

If a participant enters into the study early in pregnancy (gestational age of 5 weeks), they will have monthly visits after the 8 weeks is completed, for a maximum total of 10 visits.

Compensation will be provided in a form of a check at the end of each week during their followup visit.

WITHDRAWAL OF PARTICIPANTS

A participant will be withdrawn from the research without their consent if there is: 1) refusal to follow the medication protocol, and/or 2) refusal to answer study questionnaires, 3) the participant fails to respond to contact attempts from the study team.

RISKS TO PARTICIPANTS

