Data communication between data entry computers and database servers will be encrypted via a VPN client. Access to the VPN connection will require user authentication via username and password. Firewall software will restrict communication to traffic to the database server that is absolutely critical for conducting research. All unwanted inbound traffic will be blocked at the firewall. Anti-virus software will guard against the intrusions that typically attack through malicious email and removable media. Privacy protection and malware detection software will be active in real-time as additional assurance that unwanted cookies or browser plug-ins are not slowing performance of the device. The data management and information technology staff (data managers, programmers, statisticians) will have access to the database, but not information linking the study ID to the subject's name.

We will seek consent from our subjects to have their de-identified data and biospecimens included in the NICHD Data and Specimen Hub (DASH-https://dash.nichd.nih.gov/) for future studies.

PROVISIONS TO MONITOR THE DATA TO ENSURE THE SAFETY OF PARTICIPANTS

The primary patient and safety monitoring function is the responsibility of the PI, [name], MS. She was a founding member of the NIMH Data Safety and Monitoring Board for multi-site clinical trials. Co-Investigators are [name], and [name]. [name] is a co-PI with [name] on the Obstetric-Fetal Pharmacology Center and Medical Director of the Obstetrical Triage Service, where pregnant persons seek urgent care for sNVP. [name] is an obstetrician who works in the Obstetrical Triage Service. They will support recruitment, assessment and monitoring of subjects for the E-SNAP protocol.

The research team has the responsibility to respond to information that affects the well-being of the subject (such as severe dehydration from NVP) consistent with Good Clinical Practice. The proposed study does not limit any interventions that would be prescribed for any subject. If a subject's condition worsens during the study and her clinical status dictates removal from the study, a study physician will provide the rationale for removal. The study team will confer with the patient's primary obstetrician and to develop a treatment plan for the participant.

Adverse Events. The adverse event definitions required for an FDA IND will be applied by the study team. The occurrence of adverse events will be tracked in the study data base by

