manager [name] and statistician [name], who will be responsible for ensuring the accurate, timely and secure incorporation of information into the study data base.

In the Data Safety and Monitoring Plan, Drs. [name], [name] and [name] will evaluate safety at several levels: 1) the individual subject, 2) the group of subjects as the study data accrue through review of all adverse events for patterns, and 3) the integrity of the data and data monitoring procedures. The team will evaluate the progress of the study and provide quarterly assessments of data quality, timeliness and completion; participant recruitment; accrual and retention; participant risk versus benefit; and other factors that affect study outcome. Monitoring will include factors external to the study, such as scientific developments that could have an impact on the therapeutic options, safety of the participants or the ethics of the study. All adverse events will be reported to the Northwestern IRB, DSMB and FDA as required.

A Data Safety and Monitoring Board (DSMB) will be constructed for this project. The E-SNAP project includes pregnant persons being treated with mirtazapine, which meets the definition of a NIH clinical trial. It will also be submitted to the FDA for review for an IND, since the investigation involves pregnant persons, "a patient population that significantly increases the risk (or decreases the acceptability of the risk) associated with the use of the drug product (21 CFR 312.2(b)(1)(iii))."

The DSMB will include external academic faculty members in the following areas: one maternal-fetal medicine specialist who has expertise in reproductive outcomes associated with drug exposure; an obstetrician-gynecologist with an interest in sNVP; and a reproductive pharmacoepidemiologist. The board will conduct quarterly phone conferences to review study materials relevant to data integrity and safety as defined above. Flow through the study, side effects and adverse event frequency, withdrawals and post-enrollment hospitalizations will be reviewed. A formal Consort Chart will be generated as the study evolves.⁷⁵

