The DSMB will review specifically the frequency of adverse study-associated events in all subjects as follows: 1) acceptability data; 2) the tolerability of the mirtazapine dosage regimen; 3) mirtazapine discontinuation and reason(s) for discontinuation; 4) emergency room visits; 5) post-enrollment hospitalizations, durations and interventions; 6) additional medication exposures during the three week and optional maintenance study periods; 7) the adequacy of the tapering regimen to mitigate discontinuation symptoms, the number of pregnant persons who experience recurrence of sNVP and the number tapers that are attempted; 8) patient complaints to the study team or IRB; and, 9) reproductive outcomes for both the mother and the neonate on the Peripartum Events Scale, which will be compared to the outcomes of data from in-utero SSRI antidepressants. These findings will be evaluated and summarized by neonatology consultant [name].

The DSMB meetings will occur by teleconference. The data will be summarized and provided prior to the phone consultations to the DSMB members. The tables below summarize the activities of the DSMB.

YEAR 01	YEAR 02
Prior to initial meeting: discuss and sign agreement and expectations for DSMB participation; develop format for minutes at all meetings.	Continue quarterly teleconferences; adjust data delivery format as appropriate per DSMB input.

Initial meeting: Review protocol, establish the data to be reviewed by the DSMB; set additional quarterly phone conferences with option for as needed meetings. A particular focus will be assessment of the tolerability of the dosing strategy and the potential need for modification.	Final meeting: review course of study; summarize untoward events, quarterly phone; review and generate final report.
Quarterly: Review course of study to date, summarize any untoward events, problem solve. Data summaries provided to DSMB members at least 10 days prior to quarterly conference reviews.	

PROVISIONS TO PROTECT THE PRIVACY INTERESTS OF PARTICIPANTS

Subjects will be informed regarding staff who will have access to their data. Topics covered in questionnaires are consistent with standard of care evaluations and are not expected to induce any additional discomfort or distress.

Authorized research personnel may have access to enrolled subjects' medical records at the designation of the Principal Investigator in compliance with EDW policy.

COMPENSATION FOR RESEARCH-RELATED INJURY

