An individual subject will stop participating in the clinical trial in the instance of any of the following:

- New onset suicidal thoughts or behaviors
- Grade 3 or higher drug-related serious adverse event (SAE) based on the CTCAE, version 5.0
- Acute livery injury [alanine transaminase (ALT) or aspartate transaminase (AST) > 3-fold upper limit of normal (ULN), alkaline phosphatase (ALP) or total bilirubin (TBL) > 2 fold ULN]
- Subjects with serum sodium < 125 mmol/L

PROTECTED HEALTH INFORMATION (PHI AND HIPAA)

This study involves the creation, use or disclosure of Protected Personal Health Information. Protected Personal Health Information includes names, address, dates of birth and ages, telephone numbers, email addresses, social security numbers (see Compensation section), and medical record numbers. HIPAA requirements and measures to protect PHI will be implemented as described in the Data Management and Confidentiality section.

QUALIFICATIONS TO CONDUCT RESEARCH AND RESOURCES AVAILABLE

An interdisciplinary team with a strong commitment to improving care for pregnant persons collaborated in the development of this protocol. Northwestern is the sole clinical site for this study. The PI is [name], MS, is the Norman and Helen Asher Professor of Psychiatry and Obstetrics and Gynecology. She has conducted nine NIMH-funded R01 observational (during pregnancy) and randomized clinical trial (postpartum) studies of mood disorders. [name] was an author in the joint ACOG-APA Committee's consensus report for managing depression during pregnancy ⁷⁶ and is the first author of *Mental Health and* Behavioral Disorders, in Obstetrics: Normal and Problem Pregnancies, edited by Gabbe S et al (2007, 2012) and Psychotropic Drugs (in Schaefer C et al, Drugs during Pregnancy and Lactation: Treatment Options and Risk Assessment, 2014). She is a fellow of the American College of Neuropsychopharmacology. [name] participated in the FDA Advisory Committee to Revise Drug Labeling for Pregnancy and Lactation; FDA Pediatrics Subcommittee, Neonatal Effects of SSRI Use; Research Committee, Organization of Teratology Information Services; FDA Advisory: Perinatal Depression-Examining the Risks and Benefits of Treatment; CDC TRxeating for Two: Safe Medication Use in Pregnancy Expert Meeting. Drs. [name] and [name] (see below) are Co-PIs on the Northwestern Obstetric-Fetal Pharmacology Research Center funded by NICHD.

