Endeavor to Stop Nausea/Vomiting Associated with Pregnancy (E-SNAP) NCT05452174 09/30/2020

STATISTICAL DESIGN AND POWER ANALYSIS

Our data management team includes a highly experienced clinical trials statistician and database programmer. The REDCap management system was developed and functioning at Northwestern and is being transferred via a DUA. We are mindful of subjects' time and we send links to allow women to enter self-report measure data from home (for example, for recording of daily PUQE scores).

Analytic Approach. Descriptive statistics such as demographic and baseline clinical information will be summarized for all eligible women. These results will inform the feasibility, design and statistical approach for construction of the subsequent randomized controlled trial if the findings from the proposed study demonstrate the acceptability and feasibility of the protocol. This R21 study is not expected nor intended to have the power to address the outcomes described below, but to provide data to guide the design of a phase 3 RCT.

Aim 1. Define acceptability of mirtazapine for refractory NVP. Acceptability is defined by the number of women who accept participation compared to the total who undergo the consent procedure. All women will be asked for the reason behind their decision. A standard consort chart¹ will be created to record subject flow through the protocol. The acceptability of mirtazapine for NVP/HEG is a factor in the feasibility of the eventual RCT and is an important factor in the ability to recruit subjects and define the number of sites required.

Aim 2. Determine the tolerability and safety of the dosing regimen. Measures of tolerability include the proportions of: 1) emergent side effects on the ASE, which will be isolated by comparison to symptom ratings at intake; 2) withdrawals attributable to side effects; and 3) women who elect to continue mirtazapine after the initial 3-week trial. The daily PUQE scores will be used to evaluate the time (in days) to remission during the 3 week trial. We will use Kaplan-Meier curves to visualize time to remission (defined by a PUQE score of 3 or 4. Additionally, we will fit Cox regression models to identify factors that may be associated with time to remission.

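### Medication refusal, clinical worsening and the individual stopping rules take a woman out of the research, not only off mirtazapine, and no later PUQE, ASE or non-suicidality toxicity follow-up is stated, so missing response data may be informative

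*Protocol*

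**What the plan says.** Three parts of the Protocol end participation.

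- Withdrawal of Participants: "A participant will be withdrawn from the research without their consent if there is: 1) refusal to follow the medication protocol". The other two grounds listed there, refusing questionnaires and not responding to contact, end data collection by their nature and are not at issue.
- Trial Stopping Criteria: "An individual subject will stop participating in the clinical trial in the instance of any of the following". The list is new suicidal thoughts or behaviors, a drug-related SAE of Grade 3 or higher, acute liver injury, and serum sodium below 125 mmol/L.
- Provisions to Monitor the Data: a study physician gives the rationale when a subject's "condition worsens during the study and her clinical status dictates removal from the study", and a treatment plan is agreed with her obstetrician.

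Elsewhere the Protocol words a stop as ending drug only. Under Procedures Involved (Mirtazapine Regimen): "Mirtazapine treatment will continue unless the participant withdraws consent, experiences a limiting side effect". That sentence goes on to include an obstetrician's judgment that health risk requires discontinuation.

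Some follow-up is planned whatever the exit. On delivery outcomes, "The PES will be completed for all enrolled participants". The C-SSRS is repeated 28 days after treatment ends if it was abnormal during the trial. On safety reporting, "All adverse events will be reported to the Northwestern IRB, DSMB and FDA as required". The DSMB reviews "mirtazapine discontinuation and reason(s) for discontinuation", and also emergency visits and the durations and interventions of hospitalizations.

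In the SAP, under Aim 2: "The daily PUQE scores will be used to evaluate the time (in days) to remission during the 3 week trial". Kaplan-Meier curves and Cox models are named. There is no rule for women removed early, no missing-data method and no sensitivity analysis.

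**The concern.** Study Endpoints makes change in PUQE the primary outcome, and Aim 2 builds time to remission on the daily PUQE. Both depend on scores that stop when a woman is removed. Kaplan-Meier and Cox methods treat a censored woman as having the same prospects as those still observed. That is doubtful when toxicity or worsening caused the exit. The reasons behind medication refusal are not given, so refusal could go either way.

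The later course of a triggering toxicity also informs tolerability, which Aim 2 is meant to define. The SAP intends to weigh time to response against side effects when choosing the dose for the later randomized trial.

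**Working it through.** **The plan's own figures.** Enrolment: 20 / (1 − 0.20) = 25, as stated. SD of change: 2.1 × √2 = 2.97, as stated. The 2.3-point detectable change is conservative: a one-sample t-test with n = 20, SD 2.97 and two-sided 0.05 detects 1.96 points at 80% power. This does not bear on the point.

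**What each exit leaves in place.**

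| Exit | What ends | Later PUQE or ASE stated | Later course of the trigger stated |
|---|---|---|---|
| Medication refusal | research | no | not applicable |
| Clinical worsening | study | no | clinical treatment plan; hospitalization data to the DSMB |
| New suicidality | trial | no | yes, C-SSRS at 28 days |
| Drug-related Grade 3+ SAE | trial | no | only if hospitalized, through DSMB review |
| Liver injury, sodium < 125 | trial | no | only if hospitalized, through DSMB review |
| Limiting side effect, or obstetrician-judged health risk | drug | not spelled out, but participation does not end | not spelled out |

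The monitored taper does not fill the gap. It is offered after the initial 3 weeks, and nothing extends it to a woman removed earlier. What remains uncovered is the symptom and side-effect course, and the resolution of toxicities other than suicidality.

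**Illustration for remission.** The documents give no rate for these exits, so every input here is assumed: N = 25; k = 1 to 5 women removed and censored at day 7; 10 remissions among the others, on days 3, 5, …, 21. The top case, 5 of 25, equals the SAP's 20% dropout allowance.

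Three remissions occur by day 7, so survival there is 22/25. Then 22 − k women are at risk and 7 more remit:

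Kaplan-Meier remission at day 21 = 1 − (22/25) × (15 − k)/(22 − k).

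| k | Kaplan-Meier | If no removed woman remits, 10/25 | Error (points) | If all remit, (10 + k)/25 | Error (points) |
|---|---|---|---|---|---|
| 1 | 41.3% | 40% | +1.3 | 44% | −2.7 |
| 2 | 42.8% | 40% | +2.8 | 48% | −5.2 |
| 3 | 44.4% | 40% | +4.4 | 52% | −7.6 |
| 4 | 46.2% | 40% | +6.2 | 56% | −9.8 |
| 5 | 48.2% | 40% | +8.2 | 60% | −11.8 |

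Moving the censoring day changes the Kaplan-Meier range to 41.7% to 50.0% (day 2) or 40.9% to 45.7% (day 14).

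**Illustration for PUQE change.** Suppose the observed women improve by 2.3 points. The SAP gives that as a detectable difference and anticipates a larger one, so it is only a convenient value.

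- Removed women unchanged: 2.3 × (25 − k)/25 = 2.21, 2.12, 2.02, 1.93, 1.84 for k = 1 to 5.
- Removed women fall 6 points, from the SAP's entry score of about 10 to the remission score of 4: (2.3 × (25 − k) + 6k)/25 = 2.45, 2.60, 2.74, 2.89, 3.04.

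The observed mean stays at 2.3 throughout, so it can be too high or too low.

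**The case against.** **A reader might infer that toxicity follow-up is absent.** The documents do not support that. The C-SSRS covers the suicidality trigger, adverse events are reported, hospitalizations are reviewed with durations and interventions, and the PES covers every enrolled woman. The gap is confined to PUQE, ASE and the non-suicidality toxicities.

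**A reader might infer that any tolerability problem leads to removal.** It does not. Limiting side effects and obstetrician-judged health risk are worded as drug-only stops, and the dose can be reduced or held first. Medication refusal may be a residual category.

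**Repeated Grade 3 exits are unlikely in a completed trial.** Trial Stopping Criteria also lists a Grade 3 or higher toxicity in any organ system as a reason to stop the whole trial. This stands. The upper rows of the remission table would need mostly other kinds of exit.

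**Off-drug PUQE answers a different question.** For on-drug response, counting early stoppers as not remitted needs no further scores. This stands in part: it makes the missing SAP rule the firmer gap for that question. Following a toxicity to resolution has safety value of its own, and flagged off-drug scores are nearly free because women already enter PUQE themselves.

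**The PUQE-change illustration applies to an analysis that the SAP does not describe.** True: outside the sample size section the SAP gives no analysis of change, although the Protocol makes it the primary outcome.

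**The wording may never be reused.** The documents say that this study will guide the phase 3 design, not that its withdrawal text will carry over.

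**Conclusion.** The point holds as a minor one. Three stated rules end participation where stopping drug would do, and they would cut off the daily scores for reasons that may be related to outcome. Neither direction nor size can be established. It is tempting to conclude that remission would be overstated, but a woman who refuses further drug may have improved, and the illustration runs from 8 points too high to 12 points too low depending on what is assumed about the removed women. Its figures rest wholly on assumed numbers of exits, remissions and timing.

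No effect on the 3-week data is reported: the SAP says the study closed after 2 women, both of whom completed the 3 weeks. The SAP also disclaims power for these outcomes. The value of the correction lies mainly in any successor trial that takes up the same wording.

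**What to change.** Keep every trigger. In the Protocol's Withdrawal of Participants, Provisions to Monitor the Data and Trial Stopping Criteria (individual subject), state that medication refusal, clinical worsening and the individual stopping rules end study drug only. Unless consent is withdrawn, continue the self-entered daily PUQE to day 21, flagged as off drug, continue ASE and adverse-event collection to day 21, and follow any triggering toxicity until it resolves.

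In the SAP, include all women who took at least one dose. Add a sensitivity analysis that counts women who stop drug before remission as not remitted, so that off-drug remission from other antiemetics or the natural course is not credited to mirtazapine. In the illustration this gives 10/25 = 40% for every k.

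The cost is a few sentences in the protocol, consent form and SAP, and a few extra contacts with women who are off drug.
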